9.2.2 Unsolicited Adverse Events

Unsolicited AEs are any unsolicited unfavorable or unintended sign, symptom, disease, syndrome, abnormal laboratory finding, or concurrent illness that emerges or worsens after receipt of study vaccine relative to the subject's pre-treatment baseline, whether or not it is considered to be related to the medicinal product. The unsolicited AE reporting period begins with the day of vaccination (Day 0) through Day 42 inclusively. Additionally, any solicited AE (local or systemic) that persist beyond Day 28 will be recorded as an unsolicited AE.

Summary of descriptive statistics for unsolicited AEs (incidence of subjects with percentages and incidence of unsolicited AEs) will be presented by treatment and overall, SOC, PT, by investigator-assessed relationship (Not Related, Unlikely Related, Possible, Probable, and Definite) and severity (Mild, Moderate, and Severe). For incidence of subject calculations, each subject may only contribute once to each of the incidence rates, for an unsolicited AE following a given treatment, regardless of the number of occurrences; the highest severity or highest relationship will be presented, as appropriate.

In each table, SOC will be presented in descending order of overall incidence rate in terms of frequency of subjects and then in frequency of events (alphabetical order will be used in case of equal rates). For each SOC, PT will be presented the same way.

All unsolicited AEs will be listed.

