#### **5.1.3 Medical Monitor**

The local medical monitor is the sponsor's representative and is a licensed physician or surgeon in their country of residence. The local medical monitor reviews the safety of the product for protocols in a specific region and determines expectedness of the adverse event. The local medical monitor may make a sponsor's assessment of severity and causality for adverse events that may upgrade the degree of severity and causality determined by the principal investigator. The local medical monitor, unlike the principal investigator, is unblinded for the study.

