- **Definite** relationship to study drug (i.e., the study drug is known to be the cause of the adverse event. The evidence establishes a causal relationship; an association exists between the event and receipt of the study drug and there is a plausible mechanism for the event to be related to the study drug, and causes other than the study drug have been ruled out).

The principal investigator and the local medical monitor both determine causality. It is expected that communication and consultation may occur in the assessment of the causality of adverse events. The greatest degree of causal relationship (definite > probable > possible > unlikely related > not related) determined by either the investigator or local medical monitor after their discussions will determine the ultimate classification of the adverse event. Definite, probable and possible are considered to be related. Not related and unlikely related are considered to be unrelated.

Every effort should be made by the investigator to determine the existence of any pre-existing conditions (e.g., headache in adults or rashes in infants on Study Day 0 with onset prior to study vaccination) that must be taken into consideration when assessing causal relationship of an adverse event. Pre-existing conditions should be recorded in the CRF as baseline history and substantiated by appropriate source documentation. Intermittent conditions such as headaches in adults or irritability in infants may not be present on Study Day 0 but may represent an adverse event if the intensity or duration of the event is worse than usual following study drug.

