## **5.6 Definition of Adverse Reaction**

An adverse reaction is an adverse event judged to be related to study drug (see Section 5.3 for adverse event definition).

**Related adverse events (adverse reactions) are defined as those judged by the investigator or local medical monitor to be possibly, probably, or definitely related to study drug.**

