### **7.6.1 Adverse Events**

The safety profile of SYN023 will be described by treatment group. The primary variable for evaluation of the safety profile will be the number and percentage of unsolicited and solicited adverse events recorded at all available post-vaccination time points. For all presentations of adverse events, additional summaries based on reporting period of adverse events following each study vaccination may also be presented.

The number (percentage) of subjects with adverse events will be summarized by MedDRA system organ class (SOC) and preferred term (PT). Additional summaries will present the number (percentage) of subjects with adverse events by severity and by relationship to study drug; each subject will be counted once per preferred term at the greatest severity or most related state recorded for that term.

Separate summaries of the number (percentage) of subjects with solicited adverse events will also be presented. Solicited adverse events will also be summarized by severity and relationship to study drug; each subject will be counted once per preferred term at the greatest severity or most related state recorded for that term.

In addition, dose-safety curves may be produced to examine the proportion of subjects who experience adverse events by treatment regimen.

Serious adverse events will be recorded through the final study visit for all subjects. Listings will be provided for subjects with serious adverse events.

Listings will be provided for subjects who have discontinued prematurely due to an adverse event.

The number (percentage) of subjects with post-vaccination clinical laboratory values or vital sign values recorded as newly abnormal following study vaccination and meeting toxicity mild

criteria (Grade 1) or above as specified in the Toxicity Table (Appendix E) will be tabulated at each post-vaccination time point and overall. Clinical laboratory and vital sign abnormalities will also be reported as adverse events and will be included in the summary of adverse events.

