3.4 Subject Withdrawal and Replacement

Subjects were advised that they were free to withdraw from the study at any time. Over the course of the study, the Sponsor and Investigator or a delegate had the right to withdraw any subject from the study for one of the reasons described below; subject withdrawal will be done in accordance with inVentiv's SOP:

- Safety reason;
- non-compliance with protocol requirements;
- significant protocol deviation;

Subjects who withdraw or are withdrawn from the study after dosing will not be systematically replaced. Subjects who fail to complete the study through Study Day 28 may be replaced at the discretion of the sponsor.

4. Changes From the Protocol

For efficacy/PD analyses, AUC_{0-last} was replaced by $AUEC_{0-t}$, $AUC_{14-last}$ was replaced by $AUEC_{14-t}$, C_{max} was replaced by E_{max} , and T_{max} was replaced by $T_{max,E}$. This is standard nomenclature for such efficacy/PD parameters.

AUC_{0-inf} was removed from Efficacy/PD analyses because elimination phase cannot be calculated for rabies virus neutralizing activity (RVNA).

5. Primary and Secondary Parameters

The primary parameters will be $AUEC_{0-t}$ calculated on RVNA measured above 0.5 IU/mL. All other PD parameters will be regarded as secondary parameters (refer to Sections 10).

The safety, immunology and PK parameters will be regarded as secondary (refer to Sections 9, 11, and 12).

6. Analysis Populations

The analysis of safety and tolerability parameters will be based on the safety population detailed in Section 6.1 below. The analysis of immunogenicity (anti-SYN023 antibodies), PK, and PD parameters will be based on the Per-Protocol population detailed in Section 6.2 below.

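### SAP relationship tables use the investigator's causality call alone, while the protocol's final classification is the higher of the investigator's and the medical monitor's calls, and the departure is not declared

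*SAP*

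**What the plan says.** **Protocol.** Section 5.5 has both the principal investigator and the local medical monitor rate causality on five ordered levels. The greatest degree "determined by either the investigator or local medical monitor after their discussions will determine the ultimate classification of the adverse event". The same section sets the cut: "Definite, probable and possible are considered to be related", and the two lower levels count as unrelated. Section 5.6 defines adverse reactions as "those judged by the investigator or local medical monitor to be possibly, probably, or definitely related to study drug", so one assessor is enough. Section 5.1.3 says that the monitor's assessment "may upgrade the degree of severity and causality determined by the principal investigator". For the tables by severity and relationship, section 7.6.1 states that "each subject will be counted once per preferred term at the greatest severity or most related state recorded for that term", and does not restrict this to one assessor.

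**SAP.** Sections 9.2.1 (solicited) and 9.2.2 (unsolicited) both present events "by investigator-assessed relationship (Not Related, Unlikely Related, Possible, Probable, and Definite"), together with severity. Section 9 names no other relationship variable and does not mention the monitor's assessment or the final classification. Section 4 (Changes From the Protocol) covers only pharmacodynamic parameters: it renames them, commenting "This is standard nomenclature for such efficacy/PD parameters", and removes AUC0-inf.

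**The concern.** The protocol gives the monitor's call real force, since it can turn an unrelated event into an adverse reaction. As worded, the SAP tables ignore that call. An event that the investigator rates Unlikely Related and the monitor rates Possible would be an adverse reaction by protocol definition, yet would appear among the unrelated events in the report.

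Comparing safety is a secondary objective, and SAP section 9 plans no inferential safety analysis, so relatedness will be judged from descriptive tables and listings. A reader would take those tables to follow the protocol's definition, and nothing in SAP section 4 says otherwise.

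**Working it through.** The documents give no figure to reproduce. The check compares the two rules and counts the cases in which they disagree.

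**1. The two rules.** Order the categories Not Related < Unlikely Related < Possible < Probable < Definite. Let I be the investigator's category and M the monitor's.

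- Protocol 5.5: final category = max(I, M). The event is related if this is Possible or higher.
- SAP 9.2.1 and 9.2.2, read literally: tabulated category = I.

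The rules differ only when M is above I.

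**2. The ways M can exceed I.** Five ordered categories give 5 × 4 / 2 = 10 such pairs:

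| Upgrade | Pairs | Protocol | SAP table |
|---|---|---|---|
| Not or Unlikely Related raised to Possible, Probable or Definite | 2 × 3 = 6 | related | unrelated category |
| Upgrade within Possible, Probable, Definite | 3 × 2 / 2 = 3 | related, higher category | related, lower category |
| Not Related raised to Unlikely Related | 1 | unrelated | unrelated, lower category |

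The total is 6 + 3 + 1 = 10. Only the first group puts a protocol-defined adverse reaction in an unrelated row. These are counts of possible patterns, not of expected events.

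**3. Direction.** Since max(I, M) is never below I, the number of events at or above any given category under the SAP rule cannot exceed the number under the protocol rule. A single middle category can move either way: a Possible raised to Probable leaves the SAP with one more Possible and one fewer Probable.

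**4. Does the SAP's highest-relationship rule close the gap?** No. In 9.2.1 and 9.2.2 that rule picks the highest category over one subject's repeated occurrences of an event. It does not choose between two assessors of the same event.

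**5. Which events are exposed.** Protocol 5.7 and SAP 9.2.1 both treat solicited injection-site pain, redness and swelling as related by rule, so no upgrade can carry them across the cut. Protocol 5.7 does the same for injection-site ulceration or scarring and for axillary or localized lymphadenopathy. The gap can affect the non-local solicited events, the other local ones, and unsolicited events.

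**6. Size.** The number of affected events depends on how often the monitor upgrades, which neither document states or bounds. Each subject is counted once at the highest relationship, so an upgrade changes a row only if that subject has no other event there already rated as high.

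**The case against.** **The analysed field may already hold the final call.** Protocol 5.5 applies its rule after the two assessors have discussed the event, and under 5.3 site staff complete the adverse event form. The documents do not say whether the field called investigator-assessed holds the investigator's own rating or the agreed one. If it holds the agreed one, the tables follow the protocol and only the SAP's label is wrong. This stands as a condition on the conclusion; either way the SAP must name the source variable.

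**The investigator's call is a defensible choice.** Protocol 5.1.1 and 5.4 make the investigator responsible for causality. Section 3.4 keeps the investigator blinded to limit bias in safety assessment, while the monitor is unblinded. Protocol 7.8.2 also lets the SAP modify planned analyses. This is a good reason to keep the investigator's table, but not to drop the protocol's classification without saying so.

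**Nothing is lost from the record.** All solicited and unsolicited events are listed and serious events are listed separately. Pausing under protocol 6.1 and expedited reporting work from the assessors' judgements as events occur, not from SAP tables. That is correct and limits the consequence to the summaries.

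**Stronger readings that the documents do not support.** A reader might infer that:

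- *The relationship tables are the main safety display.* Protocol 7.6.1 makes the number and percentage of adverse events the primary safety variable; tables by relationship are additional.
- *Each upgrade lowers an arm's adverse-reaction rate by a fixed amount.* The SAP plans five separate categories, with no combined related rate and no pooled SYN023 column, and the once-per-subject rule can absorb an upgrade.
- *Every upgraded event appears as unrelated.* Only those crossing from Unlikely Related or below to Possible or above do.
- *The SAP contradicts the protocol on severity as well.* It attaches investigator-assessed to relationship only and does not say whose severity grade is used. That is a gap, not a conflict.

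**Conclusion.** The conflict is real and undeclared. Protocol 5.5 and 5.6 use the higher of two causality calls; SAP 9.2.1 and 9.2.2, as written, use one; SAP section 4 does not record the difference.

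The consequence rests on one assumption: that the analysed field is the investigator's own rating. In that case, upgrades across the cut put protocol-defined adverse reactions in unrelated rows, and upgrades within the related categories are understated. Relatedness can only be shown as equal to or lower than under the protocol. The amount cannot be estimated from the documents. No hypothesis test, sample size or reporting rule for serious events is affected. The point is worth correcting before database lock, but it does not threaten the trial's main conclusions.

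**What to change.** In SAP 9.2.1 and 9.2.2:

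- Tabulate relationship by the protocol 5.5 final classification, and name the dataset variable that holds it.
- Beside it, show the blinded investigator's assessment as the between-arm comparison, because the monitor knows the treatment and the final classification can carry that knowledge.
- List every event for which the two calls differ.
- State whose severity grade is tabulated, given the monitor's power to upgrade it under protocol 5.1.3.

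Record the choice in SAP section 4, and confirm that both causality calls are captured as separate fields.

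The cost is SAP wording, one extra set of tables, and possibly one extra adverse event data field. Subjects, visits and study procedures do not change. Showing both tables also avoids having to choose between the protocol's definition and the blinded assessment.

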9.2.3 Serious Adverse Events

A serious adverse event (SAE) is an AE meeting the outcome criteria for seriousness regardless of relationship to an administered medicinal product. SAEs are captured and recorded from the time of administration through Day 112 inclusively.

SAEs will be listed separately.

9.3 Laboratory Parameters

Clinical laboratory (serum chemistry, hematology, and urinalysis) testing will be performed at screening, on Day 0, Day 1, Day 3, Day 7, Day 14, Day 28 and Day 112. In addition Urinalysis will be performed on Day 35 and Day 42. Coagulation tests will be performed at screening, Day 0, Day 7 and Day 112.

Serum chemistry parameters should include the following: creatinine phosphokinase (CPK), troponin, total bilirubin, Aspartate aminotransferase (AST), Alanine aminotransferase (ALT), Alkaline phosphatase (ALP), creatinine, blood urea nitrogen, sodium, potassium, chloride, bicarbonate, calcium.

Hematology parameters should include the following: complete blood count with differential, hemoglobin, hematocrit, and platelet.

Coagulation parameters should include the following: Prothrombin time (international normalized ratio) (PT (INR)) and Partial thromboplastin time (PTT).

Urinalysis parameters should include the following: macroscopic examination, pH, specific gravity, protein, glucose, ketones, bilirubin, occult blood, nitrite, urobilinogen, and leukocytes. Unless otherwise specified, microscopic examination will be performed on abnormal findings only and results will be listed.

Listings of all clinical test results (serum chemistry, coagulation, hematology, and urinalysis) will be provided with the abnormal values flagged with “L” for low and “H” for high for continuous parameters, and “A” for abnormal categorical parameters.

Descriptive statistics (mean, median, SD, Min, Max, and sample size) will be presented overall for screening and by the associated current treatment for on-study measurements for each clinical laboratory test (continuous variables). Change from baseline descriptive statistics for on-study measurements will also be presented. Baseline will be defined as the last results (scheduled or unscheduled) obtained prior to the first study vaccine administration. For categorical variables (urinalysis tests), the number of subjects (frequency and percentage) will be tabulated for each individual result (e.g. negative, positive, trace). Results from repeat tests will not be included in the summary statistics unless the repeat was required (and documented as such) due to technical reasons or an invalid initial result.

A summary table of shifts from baseline to on-study measurements will be provided. Baseline will be defined in the same manner as described in the preceding paragraph for continuous variables. The shift tables will include normal, low, and high relative to the laboratory reference ranges (or normal-abnormal for categorical variables). Results from repeat tests will not be included in the summary statistics unless the repeat was required (and documented as such) due to technical reasons or an invalid initial result.

If more than one clinical laboratory is used for the study, a formula that takes into consideration the relative normal ranges of each test of laboratories used will be applied in order to normalize these data. The conversion formula used will depend on the typical distribution of the normal range for each laboratory test; the two formulae used are presented below:

- Hemoglobin, hematocrit, and platelet count test results are considered to have a normal distribution ([Chuang-Stein, 1992](#)) and the following formula will be used ([Karvanen J., 2003](#)):

$$s = L_s + (x - L_x) \frac{U_s - L_s}{U_x - L_x}$$

where U= Upper limit; L= Lower limit; s= Primary facility result; and x= Secondary facility results.

- The remaining hematology, serum chemistry, and urinalysis test results are considered to have a non-normal distribution (Chuang-Stein, 1992) and the following formula will be used (Karvanen J., 2003):

$$s = \frac{x U_s}{U_x}$$

Prior to applying these formulae, if required, units will be adjusted.

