### **7.6.2 Clinical Laboratory and Vital Sign Parameters**

For each clinical laboratory parameter and vital sign parameter prespecified in the protocol, summary statistics for continuous parameters will be presented by treatment regimen for all pre- and post-Study Drug assessments and for change from pre-Study Drug to post-Study Drug assessments.

Statistical methods: Analysis of Safety

Safety analyses will be performed using the Safety Population, as defined in Section 7.1. Count and percent summaries will be presented by treatment group for all subjects.

Descriptive statistics (number of subjects, mean, standard deviation, percent coefficient of variation, median, minimum, and maximum) will be used to summarize all safety and laboratory data.

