9.4 Vital Signs

Vital signs measurements (blood pressure, and heart rate, respiratory rate and oral temperature) will be performed at screening, on Day 0, Day 1, Day 3, Day 7, Day 14, Day 28, and Day 112.

Descriptive statistics (mean, median, SD, Min, Max, and sample size) will be presented overall for screening and by the associated current treatment for on-study measurements and each vital sign measurement. Descriptive statistics for change from baseline for on-study measurements will also be presented. Baseline will be defined as the last results (scheduled or unscheduled) obtained prior to the first study vaccine administration. Results from on-study repeat tests will not be included in the summary statistics unless the repeat was required (and documented as such) due to technical reasons or an invalid initial result.

A listing of all vital signs results will be provided.

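### SAP 9.3 and 9.4 omit, without declaring it, the protocol's count of subjects newly abnormal at toxicity Grade 1 or above, and separately omit oximetry

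*SAP*

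**What the plan says.** **Protocol.** Section 7.6.1 commits to this output: "The number (percentage) of subjects with post-vaccination clinical laboratory values or vital sign values recorded as newly abnormal following study vaccination and meeting toxicity mild", continuing "criteria (Grade 1) or above as specified in the Toxicity Table (Appendix E) will be tabulated at each post-vaccination time point and overall". It adds that such abnormalities are also to be reported as adverse events. Section 7.6.2 opens "For each clinical laboratory parameter and vital sign parameter prespecified in the protocol, summary statistics for continuous parameters will be presented". The Study Abstract (Analysis of Safety) names oximetry as one of the vital signs, and Table 3.1-1 schedules the two on a single row.

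**SAP.** Section 9.3 plans descriptive statistics with change from baseline, listings with abnormal values flagged, and urinalysis counts "tabulated for each individual result (e.g. negative, positive, trace". It also plans a shift table, for which it says "The shift tables will include normal, low, and high relative to the laboratory reference ranges". Section 9.4 begins "Vital signs measurements (blood pressure, and heart rate, respiratory rate and oral temperature) will be performed at screening" and then states "Descriptive statistics (mean, median, SD, Min, Max, and sample size) will be presented overall for screening". The same statistics are planned for change from baseline, together with a listing. Toxicity grade appears in neither section, and oximetry is not named in 9.4. Section 4 (Changes From the Protocol) lists only pharmacodynamic changes: renamed parameters and the removal of AUC0-inf.

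**The concern.** Comparing safety between the RIG and SYN023 regimens is a secondary objective. Protocol 7.6.1 chose a subject-level count against a fixed grading scale as one of the tools for that comparison, and the SAP replaces it with something different without saying so. Protocol 7.8.2 expects modified analyses to be set out in the SAP, so a reader of SAP 4 would conclude that the safety output is unchanged.

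At stake is whether the final report can say how many subjects in each arm crossed a graded threshold at each visit and at any time after dosing. Oximetry is a separate matter. It is recorded with the other vital signs and repeated every 30 minutes during the 240-minute observation on Day 0. Hypoxemia is also among the protocol's own anaphylaxis criteria (3.6.3.2). As the SAP is written, none of these readings would be summarised.

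**Working it through.** The point rests on no sample size, power or alpha, so there is no planned figure to reproduce. The check compares the texts and adds some simple arithmetic to show scale.

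**1. Promise against plan**

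| Item | Protocol 7.6.1 / 7.6.2 | SAP 9.3 / 9.4 |
|---|---|---|
| Laboratory abnormalities | n (%) newly abnormal, Grade 1 or above | Shift between normal, low and high |
| Vital-sign abnormalities | n (%) newly abnormal, Grade 1 or above | No count |
| Timing | Each time point and overall | On-study measurements; no overall or worst post-dose row specified |
| Oximetry | Summary statistics, as a prespecified vital sign | Absent |
| Declared in SAP 4 | n/a | No |

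**2. Can the shift table reproduce the promised count?** No. Appendix E starts Grade 1 at 1.1 x ULN for AST/ALT and at 1.25 x ULN for CPK. A CPK of 1.2 x ULN is therefore high in the shift table but carries no grade. For parameters graded as multiples of ULN, the high cell is at best an upper bound on the Grade 1-or-above count. The cell is also wide: AST/ALT Grade 4 lies above 10 x ULN, and 10 / 1.1 = 9.1, so values about nine-fold apart share it.

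**3. Can the other vital-sign and laboratory statistics stand in?** Only in part. Assume one subject in an arm of 40 has a diastolic pressure of 101 mm Hg (Grade 3) instead of 91 mm Hg (Grade 1). The arm mean moves by (101 - 91) / 40 = 0.25 mm Hg. For ALT at 10.1 instead of 1.1 x ULN, the mean moves by (10.1 - 1.1) / 40 = 0.225 x ULN. The mean barely registers either change. The planned maximum and the listing would show the value, but not how many subjects crossed a grade.

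**4. What do the adverse event tables cover?** Under protocol 3.6.3.5, an abnormal laboratory value that has risen in grade is reported as an adverse event. Protocol 5.4 records Grade 1 as mild, Grade 2 as moderate, and Grades 3 and 4 together as severe. SAP 9.2.2 tabulates unsolicited events by severity through Day 42. The scheduled post-dose vital-sign visits, which are also the main laboratory visits, are Days 1, 3, 7, 14, 28 and 112. Only Day 112 lies beyond Day 42. There only serious events are still collected, so a non-serious abnormality has no adverse event table to enter.

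**5. Oximetry.** The protocol schedules it at the same six post-dose visits, and the Day 0 observation adds 240 / 30 = 8 readings. Appendix E has no oximetry row, so this omission departs from 7.6.2 and is independent of the toxicity-grade table.

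**The case against.** The strongest reply is that this is secondary, descriptive output and that little information is lost. Vital signs get median, SD, minimum, maximum and change from baseline as well as means, plus a full listing. Because Appendix E vital-sign grades are absolute cut-offs, the maximum or minimum shows directly whether anyone reached Grade 3. Graded abnormalities also reach the adverse event tables by severity, fever is a solicited event counted through Day 28, and urinalysis results are tabulated level by level. The introduction to SAP 9 says adverse events will be summarised by time point. All of this stands, and it limits the size of the point.

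It does not remove the point. Protocol 7.6.1 makes adverse event reporting an addition to the graded table, not a replacement for it. The adverse event tables specified in SAP 9.2.1 and 9.2.2 name no time-point breakdown. The table shells are in a separate document not available here, but the SAP says they cover tables referred to in its text, and it refers to no graded table.

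A reader might infer three stronger conclusions that the documents do not support:

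- **That the omission is what puts a trivial and a stop-level laboratory value in one cell.** The protocol's table is a single threshold at Grade 1 or above. Restored literally, it would also pool them.
- **That no planned table carries severity, or that vital signs get means only.** The preceding paragraphs show otherwise.
- **That the pausing or stopping rules are weakened.** Those rules run on ongoing review: laboratory results are read within 72 hours (3.6.3.5), the investigator and medical monitor act under 6.1, and the safety committee can review laboratory and vital-sign data (5.1.4). The final tables do not drive them. CPK and visually read dipstick findings are exempt in any case.

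**Conclusion.** The SAP departs from the protocol in two undeclared ways: it has no Grade 1-or-above count of newly abnormal laboratory or vital-sign values, and no oximetry summary. SAP 9.4 plans no count of abnormal subjects at any of the six scheduled post-dose visits. The laboratory shift table cannot yield the promised count where grading starts above the reference limit. Adverse event tables give partial cover through Day 42, with Grades 3 and 4 merged, and none for non-serious abnormalities at Day 112. The consequence is a weaker final safety comparison than the protocol promises. No inference, and no protection of subjects during the trial, changes. The point should be corrected, but it does not threaten the study.

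This rests on two assumptions: that the unseen shells add no graded table beyond what the SAP text describes, and that adverse event collection follows the stated windows. The mean shifts shown assume 40 evaluable subjects per arm and a single extreme value.

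**What to change.** Before database lock, do one of the following.

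- **Restore.** Add to SAP 9.3 and 9.4 the protocol 7.6.1 table by arm, per visit and overall (worst post-dose value), for every parameter with an Appendix E row. Show Grade 1 or above, which is what the protocol requires. Add a Grade 3-or-above line as an improvement beyond the protocol wording, since the single threshold does not separate mild from severe values. Add oximetry to SAP 9.4 with the same descriptive statistics as the other vital signs.
- **Declare.** If either omission is intended, list it in SAP 4 with a reason.

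The data are already collected. The cost is some SAP wording and a few extra tables.
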